### 8.3.2 Treatment Procedure

- The patient's face is washed with soap and water and dried with a clean towel. The treatment area is cleansed with alcohol or Benzalkonium Chloride.
- Topical anesthetic (30% lidocaine) is applied to the injection area. Alternatively, at patient's request, an infraorbital/mental nerve block with 3% mepivacaine is used to anesthetize the treatment area.
- Restylane® Silk is administered using a thin gauge needle (30 G x ½) or a 22 gauge cannula. The needle is inserted at an approximate angle of 30° parallel to the length of the wrinkle, fold, or lip. For rhytids, Restylane® Silk is injected into the mid-to-deep dermis.
- A maximum dose of 4.0 ml is used per treatment.

### 8.3.3 Injection Technique

Restylane® Silk may be injected by a number of different techniques depending on the treating physician's experience and preference as well as the specific characteristics and needs of each patient (Restylane® Silk Package Insert). The appropriate injection method will be employed per treating investigator's discretion.

## 9 STUDY PROCEDURES

### 9.1 Visit 1: Screening Assessments

The PI and/or designee is responsible for keeping a record of all subjects screened for entry into the study as well those who did not meet the criteria, as described in Section 7, and hence were excluded.

The following procedures will be performed:

1. The PI or designee evaluates and confirms that the subject fulfills all the inclusion/exclusion criteria, as described in Section 7.

2. A written informed consent, signed by the subject as well as by the investigator or designee, is obtained.
3. Demographic information and medical history are obtained.
4. List of concomitant medications is collected.
5. Vital signs (blood pressure and pulse rate) are measured.
6. If the subject is a female of child bearing potential, a urine collection for in-clinic pregnancy test will be conducted.
7. Subject completes the SHS questionnaire
8. Subject completes the HM questionnaire.
9. Subject undergoes standardized digital photography and video of full face in accordance with the site's SOP (described in Appendix I).

## 9.2 Visit 2: Treatment

Visit 2 will take place no later than 14 days after the screening assessments. If the period between the screening assessments and the treatment is greater than 14 days, the in-clinic urine pregnancy test will be repeated for females of childbearing potential. The following procedures will be performed:

1. Subject's medical history and concomitant medications are reviewed for changes since Visit 1, Screening Assessments.
2. PI rates the subject on the OCSS and POLSS at rest.
3. The injection area is wiped with a Benzalkonium Chloride towelette.
4. A topical anesthetic containing 30% lidocaine is applied to the injection areas. Alternatively, subject may choose to receive a nerve block, infraorbital/mental with 3% mepivacaine, to numb the treatment area.
5. Subject is injected with Restylane® Silk with a volume sufficient to deliver satisfactory cosmetic results per treating investigator's discretion but not to exceed a total of 4 ml (4 syringes).
6. The volume injected is recorded.
7. The subject is monitored for any Adverse Events (AEs)

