## 7.2 Exclusion Criteria

Subjects meeting any of the following criteria will be excluded from the study:

1. Subjects who have received lip filler treatments in the past 12 months or neurotoxin injections in the past 6 months;
2. Subjects who plan to undergo neurotoxin treatments, ablative skin treatments, facial cosmetic surgery, or other injectable filler treatments during the course of the study;
3. Subjects with a known allergy or sensitivity to any component of the study ingredients;
4. Subjects with a history of bleeding disorders;
5. Female subjects who are pregnant or nursing as well as those who are of childbearing potential but do not employ adequate birth control methods;
6. Subjects with severe allergies manifested by a history of anaphylaxis or presence of multiple severe allergies;
7. Subjects with previous history of sensitivity to amide type local anesthetics;
8. Current history of chronic drug or alcohol abuse;
9. Concurrent therapy that, in the investigator's opinion, would interfere with the evaluation of the safety or efficacy of the study product;
10. Subjects who, in the investigator's opinion, have a history of poor cooperation, non-compliance with medical treatment, or unreliability; and
11. Enrollment in any active study involving the use of investigational devices or drugs.

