## 9.3 Visit 3: OCR Evaluation

The following procedures will be performed 14 ± 3 days after Visit 2, Treatment:

1. PI assesses the subject for achieving the OCR.
2. At PI's discretion, subject may receive a touch-up treatment in order to achieve OCR (not to exceed a total dose of 4 ml of Restylane® Silk).
3. A report of any AEs and changes in concomitant medications is obtained from the subject.

Subjects who require a touch-up injection will be instructed to return for the forth and final visit in 14 ± 3 days. For those who have achieved OCR, and hence do not require a touch-up injection, the following procedures will be performed:

1. Subject completes the SHS questionnaire.

2. Subject completes the HM questionnaire.
3. Subject completes a self-reported GAIS (S-GAIS).
4. PI completes the GAIS form (PI-GAIS).
5. PI rates the subject on the OCSS and POLSS at rest.
6. Subject undergoes standardized digital photography and video of full face in accordance with the site's SOP (described in Appendix I);

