### **13.2 Recording of Adverse Events**

Subjects will be instructed by the PI to immediately report the occurrence of any adverse event. Each subject should be questioned at all visits whether any side effects or adverse events have occurred. All spontaneously volunteered, inquired, and observed adverse experiences will be recorded in detail.

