## 15 APPENDICES

### Appendix A Schedule of Events

Study Visit	Visit 1: Screening	Visit 2: Treatment	Visit 3: OCR Evaluation	Visit 4: 14-Day Post-OCR	Post-Visit Evaluation
Scheduled Assessment Day	≤ -14	1	14 (±3)	28 (±3)	
Informed Consent	X				
Confirm Enrollment Criteria	X				
Demographics	X				
Photo- and Videography	X		X c	X d	
Safety Evaluations					
Medical History	X				
Vital Signs	X				
Urine Pregnancy Test a	X	X b			
Adverse Events		X	X	X	
Concomitant Medications	X	X	X	X	
Patient-Reported Outcomes					
SHS	X		X c	X d	
MH	X		X c	X d	
S-GAIS			X c	X d	
PI-Reported Outcomes					
OCSS		X	X c	X d	
POLSS		X	X c	X d	
OCR Evaluation			X		
PI-GAIS			X c	X d	
Blinded Evaluator-Reported Outcomes					
FIQ					X

a For females of child-bearing age

b If the period between Visit 1, Screening Assessments and Visit 2, Treatment is greater than 14 days

c Subjects who have achieved OCR

d Subjects who required a touch-up injection in Visit 3

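### The repeat pregnancy test rule stops at the first injection: a touch-up at Visit 3 needs no test and can follow one up to 31 days old

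*Combined protocol and SAP*

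**What the plan says.** Pregnancy is a named exclusion. Criterion 5 of Section 7.2 bars "Female subjects who are pregnant or nursing as well as those who are of childbearing potential but do not employ adequate birth control methods". At Visit 1 the site runs an in-clinic urine test in women of childbearing potential (Section 9.1, step 6).

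Section 9.2 sets the timing of the first injection, "Visit 2 will take place no later than 14 days after the screening assessments", and then provides for a longer gap: "If the period between the screening assessments and the treatment is greater than 14 days, the in-clinic urine pregnancy test will be repeated". Footnote b of Appendix A states the same trigger with the visits named: "If the period between Visit 1, Screening Assessments and Visit 2, Treatment is greater than 14 days". The pregnancy test row of Appendix A is marked at Visit 1 and, conditionally, at Visit 2. It has no mark at Visit 3 or Visit 4.

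Visit 3 falls 14 ± 3 days after Visit 2. Under Section 9.3 the "subject may receive a touch-up treatment in order to achieve OCR", at the investigator's discretion. Section 6 describes this as a second injection of the product. The other checks that Section 9.3 lists for a touch-up subject are the assessment of cosmetic result and a report of adverse events and medication changes. No pregnancy test is listed.

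**The concern.** The plan treats a test more than 14 days old as needing repetition before the first injection, but sets no such condition before the second. Footnote b closes off the reading that the word treatment in Section 9.2 also covers the touch-up, because it names Visit 2.

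The plan's other safeguards do not fill the gap. Eligibility, including birth control, is confirmed once: at Visit 1, "The PI or designee evaluates and confirms that the subject fulfills all the inclusion/exclusion criteria", and the Appendix A row "Confirm Enrollment Criteria" is marked only there. Section 13.2 says "Each subject should be questioned at all visits whether any side effects or adverse events have occurred", but neither that question nor the medication question would detect a pregnancy the subject does not know about. In Section 9.3 both come after the touch-up step.

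A subject who conceived around or after screening could therefore be re-injected untested, at a site following the plan to the letter. What is at stake is subject safety; no endpoint, estimate or test depends on it.

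**Working it through.** The plan gives no figure for the age of the test at a touch-up, so there is none to reproduce. The check is arithmetic on the visit windows.

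**Inputs**

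- *g*, days from Visit 1 to Visit 2: 0 to 14 where the test is not repeated (Section 9.2).
- *d*, days from Visit 2 to Visit 3: 14 ± 3, so 11 to 17 (Section 9.3).
- Trigger for a repeat at Visit 2: *g* greater than 14 (Section 9.2; Appendix A, footnote b).

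**Formula**

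Age of the latest test at touch-up = *g* + *d* with no repeat at Visit 2. After a repeat at Visit 2 the clock restarts and the age is *d* alone.

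**Results with the Section 9 windows**

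| Case | Youngest (days) | Oldest (days) |
|---|---|---|
| No repeat, *g* = 0 | 0 + 11 = 11 | 0 + 17 = 17 |
| No repeat, *g* = 4 | 4 + 11 = 15 | 4 + 17 = 21 |
| No repeat, *g* = 14 | 14 + 11 = 25 | 14 + 17 = 31 |
| No repeat, all *g* | 11 | 31 |
| Repeated at Visit 2 | 11 | 17 |

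A gap of 4 days is the smallest at which all seven permitted Visit 3 days put the test past 14 days; at *g* = 3 the earliest Visit 3 gives 3 + 11 = 14, which is not past it. After a repeat at Visit 2, only days 15, 16 and 17 exceed 14.

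**Does another reading of the windows change this?**

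1. *Appendix A day labels.* Treatment is Day 1 and Visit 3 is Day 14 ± 3, so *d* = (11 to 17) − 1 = 10 to 16. Every age drops by one day: 10 to 30 without a repeat, 10 to 16 after one. The smallest gap at which every Visit 3 day exceeds 14 becomes 5 (5 + 10 = 15). After a repeat, days 15 and 16 still exceed 14.
2. *The Appendix A screening entry of ≤ -14.* If this means Day -14 or earlier, a gap above 14 days triggers the repeat and the age is 11 to 17. A gap of exactly 14 days does not trigger it, and the age is 25 to 31.

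Under each reading some permitted touch-up follows a test more than 14 days old. These are ranges of permitted schedules, not frequencies; no schedule is assumed more likely than another.

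**The case against.** The plan states no general maximum age for a pregnancy test. Its 14-day rule follows directly on the 14-day cap for Visit 2 and can be read as a contingency for late treatment, so carrying it over to the touch-up infers a purpose. The 31-day figure needs both the latest screening gap and the latest Visit 3. With same-day screening or a repeat at Visit 2, and Visit 3 on its nominal day, the test is 14 days old and the plan's own trigger would not be met. The documents describe no specific hazard of this approved filler in pregnancy. There are also partial safeguards: the birth control requirement, the review of medical history at Visit 2, the instruction to report adverse events at once, the investigator's discretion over the touch-up, and the investigator's general duty of care (Section 14.8).

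Much of this is fair. The frequency is unknown, 31 days is an extreme, and no rule is broken by a site that omits the test. But the conclusion does not rest on the extreme: any unrepeated gap of 4 days or more passes 14 days on every permitted Visit 3 day (5 by the Appendix A labels). None of the safeguards is a test. The plan asks for a retest at Visit 2 despite the same birth control exclusion, so it does not itself treat contraception as a substitute. It gives no reason for exempting the second injection.

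**Conclusion.** The concern holds. The retest rule covers the first injection only, and a touch-up can be given on a test 11 to 31 days old (10 to 30 by the Appendix A labels), or 11 to 17 days old after a repeat at Visit 2 (10 to 16).

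This assumes that visits fall within the stated windows and that the site does only the tests listed; an investigator could test voluntarily. The plan gives neither the share of women of childbearing potential nor the touch-up rate, so the number exposed cannot be estimated. It is a gap in the scope of a safety rule that should be closed because closing it is cheap. It has no bearing on the statistical analysis.

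**What to change.** Extend the existing rule to the second injection:

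- Reword footnote b of Appendix A, and the matching sentence in Section 9.2, so that the 14 days run from the last pregnancy test to each injection session.
- Add a mark with footnote b in the Visit 3 column of the pregnancy test row, for touch-up subjects of childbearing potential.
- Add a line to Section 9.3, ahead of the touch-up step, requiring the test when the last one is more than 14 days old.

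In the same edit, reconcile the ≤ -14 screening entry in Appendix A with the 14-day cap in Section 9.2, and settle whether a longer gap is allowed. This is a wording repair and the finding does not depend on it.

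The document cost is a few words in Section 9.2 and footnote b, one table cell, one new line and one clarified window. The running cost is one in-clinic urine test for each touch-up subject of childbearing potential whose last test is more than 14 days old.

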## 9.3 Visit 3: OCR Evaluation

The following procedures will be performed 14 ± 3 days after Visit 2, Treatment:

1. PI assesses the subject for achieving the OCR.
2. At PI's discretion, subject may receive a touch-up treatment in order to achieve OCR (not to exceed a total dose of 4 ml of Restylane® Silk).
3. A report of any AEs and changes in concomitant medications is obtained from the subject.

Subjects who require a touch-up injection will be instructed to return for the forth and final visit in 14 ± 3 days. For those who have achieved OCR, and hence do not require a touch-up injection, the following procedures will be performed:

1. Subject completes the SHS questionnaire.

2. Subject completes the HM questionnaire.
3. Subject completes a self-reported GAIS (S-GAIS).
4. PI completes the GAIS form (PI-GAIS).
5. PI rates the subject on the OCSS and POLSS at rest.
6. Subject undergoes standardized digital photography and video of full face in accordance with the site's SOP (described in Appendix I);

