**Study Duration**

Subjects will be followed for 14 days after a treatment that has produced Optimal Cosmetic Results.

---

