## 6 STUDY DESIGN

This is an open-label, post-market study to assess the impact of lip rejuvenation with Restylane® Silk on the projected first impression and the self-perception of mood.

20 subjects, at least 21 years of age, who display mild to severe oral commissures or none to severe perioral lines, as judged by the Principal Investigator (PI) utilizing the Oral Commissure Severity Scale (OCSS, Appendix G) or the Perioral Lines Severity Scale (POLSS, Appendix H), will be enrolled.

The study is composed of up to 4 patient visits and a post-visit evaluation of patients' photographs by blinded evaluators. A schematic of the study design is presented in Appendix A.

All subjects who meet the specified criteria, listed in Section 7, will complete the Subjective Happiness Scale (SHS, Appendix B) and the Happiness Measures questionnaire (HM, Appendix C) prior to receiving any treatments. The PI also records the severity of subjects' oral commissures and/or the perioral lines using the OCSS and/or the POLSS respectively. Furthermore, all subjects undergo photo- and videography, as described in Appendix I, prior to treatment.

Subjects will then be injected with Restylane® Silk with a volume sufficient to achieve Optimal Cosmetic Results (OCR), per treating investigator's discretion but not to exceed a total of 4ml (4 syringes). Subjects will be assessed 14 ± 3 days after injection for achieving the OCR. If OCR has not been reached, as judged by the PI, a second, 'touch-up,' injection of Restylane® Silk will be performed.

The final evaluation of subjects will take place 14 ± 3 days after achieving OCR. Hence, this would be 14 ± 3 days after the first injection for those who achieved OCR with one treatment but 28 ± 3 days after the first injection for those who required a 'touch-up' injection. Subjects will complete the SHS and HM questionnaires as well as self-report any aesthetic alterations experienced using the Global Aesthetic Improvement Scale (GAIS, Appendix D). They will also undergo photo- and videography, as described in Appendix I. Furthermore, the PI will rate the subjects on the GAIS (Appendix E) as well as on the OCSS and the POLSS.

Photographs taken at pre-treatment and 14-Day Post-OCR will be randomly divided into 4 binders, for a total of 10 photographs per binder. Each binder will be evaluated at least by 50 blinded evaluators using the First Impressions Questionnaire (FIQ, Appendix F) to rate each photograph.

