#### **9.4 Visit 4: 14-Day Post-OCR**

Visit 4 will take place 14 ± 3 days after Visit 3, OCR Evaluation only for subjects who required a touch-up injection in Visit 3 in order to achieve OCR.

The following procedures will be performed:

1. Subject completes the SHS questionnaire.
2. Subject completes the HM questionnaire.
3. Subject completes a self-reported GAIS (S-GAIS).
4. PI completes the GAIS form (PI-GAIS).
5. PI rates the subject on the OCSS and POLSS at rest.
6. Subject undergoes standardized digital photography and video of full face in accordance with the site's SOP (described in Appendix I);
7. A report of occurrence of any AEs and changes in concomitant medications is obtained from the subject.

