### 12.2 Study Population

The study population will include all subjects who are enrolled and have received treatment. The entire study population will be included in the statistical analyses.

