### 12.3 Study Endpoints

#### 12.3.1 Primary Endpoints

1. FIQ completed by 200 blinded evaluators using the photos of subjects from the baseline and the 14-Day Post-OCR visits
2. Subjects' execution of the SHS at 14-Day Post-OCR
3. Subjects' completion of the HM questionnaire at 14-Day Post-OCR

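### Post-treatment primary assessments are tied to reaching OCR or requiring a touch-up, so a treated subject short of OCR who gets no touch-up has no clear assessment visit, although Section 12.2 analyses all treated subjects

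*Combined protocol and SAP*

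**What the plan says.** **Touch-up rule.** Section 6 reads as mandatory: "If OCR has not been reached, as judged by the PI, a second, 'touch-up,' injection of Restylane® Silk will be performed". Section 9.3 leaves it to the PI: "subject may receive a touch-up treatment in order to achieve OCR (not to exceed a total dose of 4 ml".

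**Volume limit.** Sections 6, 9.2 and 9.3 each state 4 ml as a total, and Section 9.2 allows all of it at Visit 2. Section 8.3.2 states 4.0 ml per treatment.

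**Who is assessed after treatment.** SHS, HM, S-GAIS, PI-GAIS, OCSS, POLSS and photographs are listed for two groups.
- Visit 3 (Section 9.3): "For those who have achieved OCR, and hence do not require a touch-up injection, the following procedures will be performed". Footnote c of Appendix A carries the same condition.
- Visit 4 (Section 9.4): "only for subjects who required a touch-up injection in Visit 3 in order to achieve OCR". Footnote d of Appendix A has "Subjects who required a touch-up injection in Visit 3".

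Section 9.3 also says that subjects who require a touch-up will be told to come back for the final visit in 14 ± 3 days.

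**Timing.** The synopsis, under Study Duration, has "Subjects will be followed for 14 days after a treatment that has produced Optimal Cosmetic Results". Section 6 likewise counts the final evaluation from the achievement of OCR.

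**Analysis.** The study population in Section 12.2 is every enrolled and treated subject, and "The entire study population will be included in the statistical analyses". The first primary endpoint in Section 12.3.1 is the FIQ "using the photos of subjects from the baseline and the 14-Day Post-OCR visits"; the other two are SHS and HM at the same time point. Sections 12.2 and 12.4 give no rule for a missing post-treatment value.

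**The concern.** All three primary endpoints need a post-treatment photograph, SHS or HM. As written, whether these are collected can depend on the PI's open-label judgement that the cosmetic result is optimal, or on a touch-up being given. Any subjects who fall between the two lists are those the PI judged to have the poorer result, so the loss would not be random with respect to cosmetic outcome.

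If cosmetic result is related to first impression or mood, the before-after change in the remaining subjects would be shifted towards the hypothesis. In a single-arm study no comparison group would reveal it. Whether that relation exists is what the secondary objective in Section 5 sets out to examine, so it cannot be taken as given. A subject who never reaches OCR also has no defined endpoint time, because the endpoints are set at 14-Day Post-OCR.

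**Working it through.** **1. The plan's own figure.** Section 12.1 gives a difference of 2.5, SD 14, N = 20, α = 0.05 and power of about 8%. For two independent groups of 20, two-sided, normal approximation: SE = 14 × √(2/20) = 4.43; 2.5/4.43 = 0.565; power = Φ(0.565 − 1.96) = 8.1%. The figure reproduces and is not in dispute. It matters here only because it shows how the SD of 14 was used (step 5).

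**2. Volume left for a touch-up.** If the total in Section 9.3 is cumulative, the volume left after v ml at Visit 2 is 4 − v: 3, 2, 1 and 0 ml for v = 1, 2, 3 and 4. At v = 4, a subject short of OCR cannot have the touch-up that Section 6 says will follow. Section 6 states the 4 ml total shortly before its touch-up sentence, so this tension lies within Section 6 as well as between Sections 6 and 9.3. Under the per-treatment wording of Section 8.3.2, volume would remain.

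**3. Which list each subject falls on.**

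| Status at Visit 3 | Visit 3 list | Visit 4 list |
|---|---|---|
| OCR reached | yes | no |
| Short of OCR, touch-up given | no | yes, even if still short of OCR afterwards (the Section 9.4 list has no OCR condition) |
| Short of OCR, no touch-up (PI discretion or limit reached) | no | only if *required* means needed |

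For the third row the text points both ways. The Section 9.3 instruction to return is addressed to those who require a touch-up, which favours *needed*. The Section 9.4 phrase ties the touch-up to Visit 3 and to the purpose of achieving OCR, which favours *given*.

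**4. Effect on the photograph layout.** Section 6 plans 4 binders × 10 photographs = 40 = 20 subjects × 2. With k subjects lacking a post-treatment photograph, 40 − k remain: 39, 38 or 36 for k = 1, 2 or 4. If their baseline photographs are also dropped, 40 − 2k remain: 38, 36 or 32.

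**5. Size of a possible shift.** The general form is (k/20) × (mean change in assessed − mean change in unassessed). The documents give neither k nor the second mean. As an illustration, assume that assessed subjects change by the protocol's 2.5 FIQ points and unassessed subjects by 0. The mean over all treated is 2.5 × (20 − k)/20, and the assessed-only mean overstates it by 2.5 × k/20.

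| k | Mean over all 20 | Overstatement | Relative, k/(20 − k) | SE = 14/√(20 − k) | Shift/SE |
|---|---|---|---|---|---|
| 1 | 2.375 | 0.125 | 5.3% | 3.21 | 0.04 |
| 2 | 2.25 | 0.25 | 11.1% | 3.30 | 0.08 |
| 4 | 2.0 | 0.5 | 25.0% | 3.50 | 0.14 |

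This SE takes 14 as the SD of the change. On the two-group basis that reproduces the 8%, SE = 14 × √(2/(20 − k)) = 4.54, 4.67 and 4.95, and the shift is 0.03, 0.05 and 0.10 of an SE.

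**The case against.** The strongest reply is that the two lists were meant to cover everyone. Section 9.3 links having no need of a touch-up to having reached OCR, and Section 6 supplies the converse. The Visit 4 trigger is worded as *require* or *required*, so a subject who needed a touch-up and did not get one would still return. If Section 6 governs without exception, the uncovered group is empty. This reading is reasonable, but Section 9.3's discretion and the wording of Section 9.4 keep it from being secure. A protocol should not leave the collection of primary outcomes to that choice of reading.

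Three stronger readings are tempting, and the documents do not support them.
- A reader might infer that Section 6 sets no volume limit and only Section 9.3 does. Section 6 states the 4 ml total itself; the differences are mandatory against discretionary, and total against per treatment.
- A reader might infer that subjects short of OCR definitely go unassessed, or that some are short of OCR yet judged not to need a touch-up and so are on neither list under any reading. The documents describe no such group, and those who receive a touch-up are assessed whatever its result.
- A reader might infer that the results will be biased towards the hypothesis. The direction depends on an unproven relation, and k may be 0.

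It is also fair that any dropout would upset the 40-photograph layout, and that Section 12.4 requires n to be reported for continuous data, so a loss would be visible.

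**Conclusion.** The point holds as a gap in the wording on who is assessed and when, together with an unreconciled touch-up rule and volume limit. It does not show that primary data will be lost or that the conclusion will be biased.

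The number affected is not given and may be 0. For 1 to 4 subjects the illustrative shift is 0.125 to 0.5 FIQ points, at most about 0.14 of a standard error. That rests on an assumed zero change in the unassessed and on 14 being the SD of the change. A shift of that size would matter little beside the sampling error of a study planned at about 8% power. The reason to act is that primary outcome collection should not be able to depend on an open-label judgement of treatment success, and separating the two costs little.

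**What to change.** Make outcome collection independent of the OCR judgement.
- Collect SHS, HM, S-GAIS, PI-GAIS, OCSS, POLSS and photographs at Visit 3 from every subject who leaves without a touch-up, and at Visit 4 from every subject who received one.
- Change the conditions in Sections 9.3 and 9.4 and in footnotes c and d of Appendix A to match.
- In Sections 6, 9.5, 10.1 to 10.2.4, 12.3.1 and 12.3.2, define the endpoint time as this final assessment, about 14 days after the last injection, rather than only as 14-Day Post-OCR. Without this step, a subject never at OCR would be measured but would have no defined endpoint time.
- Report the number of treated subjects not at OCR.

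Separately, the sponsor and investigator must reconcile Sections 6, 8.3.2, 9.2 and 9.3 on whether the touch-up is mandatory or discretionary and on the scope of the 4 ml limit. No view is taken here on which is right.

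Cost: a short amendment, which under Section 14.1 needs sponsor and IRB approval, and one added set of assessments for each such subject. No visit is added, because these subjects already attend Visit 3, and the assessment change leaves treatment decisions untouched.
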